3.4.2 Dose constraints

Dose will be prescribed to 100%.

Max dose in PTV (highest dose PTV per plan): goal 107%, tolerated 115%

Min dose in PTV goal 95%

Contoured organs at risk: Bladder, bladder minus CTV, rectum, small bowel, femoral heads, penile bulb

DOSE LEVEL 1: 20 fractions

Normal organ limit Dose level 1: 20 fractions	No more than 50% volume receives dose that exceeds	No more than 70% volume receives dose that exceeds
Bladder minus CTV	52.6 Gy	33.8 Gy

Normal organ limit Dose level 1: 20 fractions	No more than 15% volume receives dose that exceeds	No more than 25% volume receives dose that exceeds	No more than 35% volume receives dose that exceeds	No more than 50% volume receives dose that exceeds
Rectum	60.0 Gy	56.2 Gy	52.6 Gy	48.2 Gy

Small bowel: V38 < 195cc (peritoneal cavity)

Femoral heads: No more than 10% to 45 Gy

DOSE LEVEL 2: 15 fractions

Normal organ limit Dose level 2: 15 fractions	No more than 50% volume receives dose that exceeds	No more than 70% volume receives dose that exceeds
Bladder minus CTV	47.8 Gy	31.1 Gy

Normal organ limit Dose level 2: 15 fractions	No more than 15% volume receives dose that exceeds	No more than 25% volume receives dose that exceeds	No more than 35% volume receives dose that exceeds	No more than 50% volume receives dose that exceeds
Rectum	54.4 Gy	51.1 Gy	47.8 Gy	44.5 Gy

Small bowel: V35 < 195cc (peritoneal cavity)

Femoral heads: No more than 10% to 42 Gy

DOSE LEVEL 3: 10 fractions

Normal organ limit Dose level 3: 10 fractions	No more than 50% volume receives dose that exceeds	No more than 70% volume receives dose that exceeds
Bladder minus CTV	41.4 Gy	27.5 Gy

Normal organ limit Dose level 3: 10 fractions	No more than 15% volume receives dose that exceeds	No more than 25% volume receives dose that exceeds	No more than 35% volume receives dose that exceeds	No more than 50% volume receives dose that exceeds
Rectum	46.8 Gy	44.1 Gy	41.4 Gy	38.7 Gy

Small bowel: V30 < 195cc (peritoneal cavity)

Femoral heads: No more than 10% to 36 Gy.

3.5 FOLLOW UP

After treatment completion, patients will be invited to Clinical center or referred to their local provider for follow up visit 1 month and 3 month post treatment, and subsequently every 3 months for 2 years. For evaluations during these visits, please, see Study Calendar [3.3](#).

3.6 COST AND COMPENSATION

3.6.1 Costs

NIH does not bill health insurance companies or participants for any research or related clinical care that participants receive at the NIH Clinical Center. If some tests and procedures are performed outside the NIH Clinical Center, participants may have to pay for these costs if they are not covered by an insurance company. Medicines that are not part of the study treatment will not be provided or paid for by the NIH Clinical Center.

3.6.2 Compensation

Participants will not be compensated on this study.

3.6.3 Reimbursement

The NCI will cover the costs of some expenses associated with protocol participation. Some of these costs may be paid directly by the NIH and some may be reimbursed to the participant/guardian as appropriate. The amount and form of these payments are determined by the NCI Travel and Lodging Reimbursement Policy.

3.7 CRITERIA FOR REMOVAL FROM PROTOCOL THERAPY AND OFF STUDY CRITERIA

Prior to removal from study, effort must be made to have all subjects complete a safety visit approximately 30 days following the last dose of study therapy.

3.7.1 Criteria for removal from protocol therapy

- Completion of protocol therapy
- Participant requests to be withdrawn from active therapy
- Unacceptable Toxicity as defined in section [3.1.1](#)
- PI discretion

3.7.2 Off-Study Criteria

- Completed study follow-up period
- Participant requests to be withdrawn from study
- Death
- Recurrence of prostate cancer
- PI discretion
- Non-compliance with follow-up visits or protocol mandated procedures
- PI decision to close the study
- Lost to follow up

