3.1.1 Dose Limiting Toxicity

The DLT period includes treatment period (4, 3 or 2 weeks depending on Dose Level) and the 3 following weeks. DLT is defined as any of the following:

- Grade 3 rectal, small bowel, or urinary toxicity that does not resolve to Grade 2 or less within 4 days with appropriate medical management.
- Other grade 3 in-field toxicities attributable to RT that do not resolve to Grade 2 or less within 4 days with medical management.
- Delays of more than one week in completing radiation treatment due to toxicity (cumulative duration of delay over the course of the entire treatment).

Additionally, toxicities that occur more than 3 weeks after completion of treatment and during the 24 month follow up period will be followed and scored but will not be used for escalation with the following exception. If Grade ≥ 4 late bowel or bladder injury is observed in 2 patients at any Dose level, dose escalation will be terminated and the dose below that dose level in which the toxicity was observed will be considered the MTD. Early and late toxicities used for assessment of DLTs should be attributable (possible, probable or definite) to radiation. Changes in sexual and erectile function will not be considered a DLT. MTD will be determined for each Arm separately.

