7. +/- 1 week for 1 month visit, +/- 2 weeks for 3 and 6 month visits. +/- 4 weeks for next visits. If subjects are not able or willing to come to NIH to FU visits, they will be followed every three months remotely (by phone call, e-mail for adverse events or other NIH approved remote communication platform), further tumor therapy and lab results. Lab results from outside laboratories are accepted. A clinical evaluation may be completed remotely with a member of the study team to determine if the physical exam, vital signs and ECOG may be omitted. A subject may be referred to a local providers for further assessment at the discretion of the investigator after a remote assessment (e.g., finding that requires clinical assessment/follow up). Subjects may also be referred to their local provider for labs. If biochemical failure per **6.3.1** is identified, the second measurement will be obtained for confirmation, ideally at the NIH Clinical Center. Imaging may be delayed, but will be completed as soon as feasible. Collection of research blood or urine will be omitted or collected in a delayed fashion.
8. Only at the 6 month follow up time point.
9. Scans may be omitted if eligibility can be determined from MRI or other imaging results including 18F-DCFPyL.

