8.1.2 Secondary Objectives

- Define the toxicity profile of image guided, hypofractionated, focally dose escalated post-prostatectomy radiation. Assessment of acute toxicities for dose escalation will occur through 3 weeks after radiation.
- Describe the rate of PSA control (biochemical progression free survival, bPFS) at 1 and 2 years after treatment with image guided, hypofractionated, focally dose escalated post-prostatectomy radiation. We hypothesize that the rate of PSA control (bPFS) will compare favorably to the rate obtained with salvage radiation previously published series.
- Describe the effects of image-guided, focally dose escalated prostate bed radiation on patient reported outcomes (SHIM, AUA Symptom Index, EPIC-26). We hypothesize a reduction in quality of life (urinary and gastrointestinal) after radiation that persists for several months but returns to baseline in most patients by 2 years after treatment. We hypothesize that erectile dysfunction will progress without improvement over time.

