8.4.5 Exploratory Analyses

- Evaluate decision regret at the time of enrollment and at the end of follow up relating to the primary treatment for prostate cancer to determine if successful salvage mitigates decision regret. The percentage of patients scored as having decision regret will be compared to the percentage of patients not exhibiting decision regret (regarding the initial surgery). It is hypothesized the effective salvage therapy will mitigate decision regret expressed at the time of enrollment.
- Explore candidate biomarkers of radiation toxicity in blood and urine of patients receiving image-guided, hypofractionated, focally dose escalated post-prostatectomy radiation. Protein and metabolic biomarkers will be assessed in collected specimens.
- Explore MRI imaging parameters of erectile tissues in regards to testosterone and erectile dysfunction. MRI imaging of erectile tissue will be compared to evaluate for changes in volume and tissue characteristics after radiotherapy.
- To compare dosimetry of standard compared to biological optimization algorithms for treatment planning of post-prostatectomy radiation. Treatment planning will be optimized

with both approaches to allow comparison of normal tissue complication probability curves. Results will be reported in a descriptive fashion.

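### Recurrence takes a patient off study with no exception for late-toxicity or questionnaire follow-up, which conflicts with the 24-month data the plan relies on

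*Combined protocol and SAP*

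**What the plan says.** Section 3.7.2 lists "Recurrence of prostate cancer" among the off-study criteria, beside death, withdrawal and loss to follow-up. Removal from protocol therapy has its own list in 3.7.1, so this criterion ends study participation, not only treatment. Section 3.7.2 does not define recurrence. Section 6.3.2 uses the term biochemical recurrence for PSA above 0.1 confirmed by a second rising value at least a month later.

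The only contact that section 3.7 asks for before removal is early: "effort must be made to have all subjects complete a safety visit approximately 30 days following the last dose of study therapy".

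Other sections need data well after that:

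- Section 3.1.1: "toxicities that occur more than 3 weeks after completion of treatment and during the 24 month follow up period will be followed and scored". These toxicities do not affect escalation, with one exception: "If Grade ≥ 4 late bowel or bladder injury is observed in 2 patients at any Dose level", escalation ends and the level below becomes the MTD. Section 8.4.4 repeats this and defines late as more than 90 days after radiotherapy.
- Section 3.3, footnote 4, schedules questionnaires every 6 months to month 24. Section 8.1.2 expects a urinary and bowel decline that "persists for several months but returns to baseline in most patients by 2 years after treatment".
- Sections 1.1.3 and 8.4.5 assess decision regret at enrollment and at the end of follow-up: "It is hypothesized the effective salvage therapy will mitigate decision regret expressed at the time of enrollment".
- Section 3.3, footnote 7, provides remote contact every three months for patients unable or unwilling to attend. It covers adverse events and "further tumor therapy and lab results".

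**The concern.** A patient who has left the study cannot supply month-24 questionnaires, an end-of-follow-up regret score or a report of a new late injury. The safety visit at about 30 days falls before the late period begins, so it cannot stand in for late follow-up.

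The loss is also tied to outcome, because the patients removed are those whose salvage treatment failed. Two-year patient-reported results, a secondary objective, would lean towards patients with controlled disease. The regret analysis would have little late information on unsuccessful salvage. A late Grade 4 or higher bowel or bladder injury arising after recurrence would not count towards a rule that can set the MTD, the primary endpoint.

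**Working it through.** **1. The plan's own figure.** Section 8.2 gives a maximum of 48. Two arms × (3 levels × 6 patients + 6 in expansion) = 48, or 24 per arm. The minimum is 2 × 2 = 4. Both reproduce, and nothing here disputes them.

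**2. How many could leave.** The documents give no expected failure rate for this trial. The background cites external series: 62-80% progression-free at 5 years (1.2.1) and 67% at 4 years (1.2.2). Assume that recurrence means biochemical recurrence and that the hazard is constant. Then 2-year failure = 1 − S^(2/t).

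| Cited rate | 2-year failure | Of 24 | Of 48 |
|---|---|---|---|
| 80% at 5 years | 1 − 0.80^(2/5) = 8.5% | 2.0 | 4.1 |
| 62% at 5 years | 1 − 0.62^(2/5) = 17.4% | 4.2 | 8.4 |
| 67% at 4 years | 1 − 0.67^(2/4) = 18.1% | 4.4 | 8.7 |

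With 5-year rates of 80% and 62%, the chance that a six-patient level loses at least one patient is 1 − 0.80^(12/5) = 41% and 1 − 0.62^(12/5) = 68%.

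**3. Late follow-up kept.** With monthly hazard h = −ln(1 − f)/24, the share of months 3-24 still observed is (e^(−3h) − e^(−24h))/(21h). This gives 95.1% for f = 8.5% and 89.9% for f = 17.4%.

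**4. Effect on the late rule.** For a true late Grade 4 or higher rate p (an assumption), the chance of at least two events in six patients is 1 − (1−p)^6 − 6p(1−p)^5. If events are spread evenly over months 3-24 and are independent of failure, leaving at failure replaces p by p × the share kept.

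| Assumed p | Full follow-up | f = 8.5% | f = 17.4% | Loss, points |
|---|---|---|---|---|
| 10% | 11.4% | 10.5% | 9.5% | 0.9-1.9 |
| 20% | 34.5% | 32.1% | 29.5% | 2.4-4.9 |
| 30% | 58.0% | 54.8% | 51.2% | 3.2-6.8 |

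Lower rates: section 1.2.1 reports late Grade 3 or higher toxicity with contemporary techniques as 7% genitourinary and 2% gastrointestinal. Their sum, 9%, is a generous ceiling for Grade 4 or higher under that treatment. At p = 9% the chance falls from 9.5% to between 8.7% and 7.9%. At p = 2% it falls from about 0.6% to about 0.5%.

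Sensitivity: if every late event came at month 24, p would be multiplied by 1 − f. The loss for p of 10-30% would then be 1.6-11.9 points. If 2-year failure were 30% (an assumption), the even-spread figure at p = 20% would be 25.8%, against 34.5%.

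**5. What is not affected.** The DLT window closes 3 weeks after treatment, and the first scheduled post-treatment PSA is at month 3, so acute DLT assessment is complete before a scheduled PSA can trigger removal. Confirmed PSA failure is itself a bPFS event, so leaving at that point costs that estimate nothing.

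**6. Whether another section cures the conflict.** Footnote 7 covers patients who cannot or will not attend; it does not say that it applies after a patient goes off study. Section 6.1 follows recorded adverse events to baseline or stabilization, but that does not reach new late events after removal. Section 8.4.3 specifies a mixed model for quality of life and does not address data missing after recurrence.

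**The case against.** The strongest reply is that the practical loss is small and the trigger uncertain. Much of this stands.

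- Section 3.7.2 does not say biochemical. If only clinical recurrence is meant, fewer patients leave. The failure rates are external, the constant hazard is assumed, and Arm 2 includes adjuvant patients to whom salvage rates do not directly apply. Section 8.2 itself calls the sample size likely over-estimated. The counts in step 2 are therefore upper-end illustrations.
- A reader might infer that two-year quality of life is estimated only in controlled patients. The plan does not do that: the mixed model in 8.4.3 uses every score obtained before a patient leaves. The concern is outcome-dependent dropout, not exclusion.
- A reader might infer that the regret question cannot be answered. The scale is given at baseline and every 6 months, so patients who fail after month 6 have post-treatment scores. Change within controlled patients also bears on the stated hypothesis. What is weakened is the end-of-follow-up comparison with unsuccessful salvage, and the objective is exploratory.
- A reader might infer that the late rule is disabled. At the cited failure rates it keeps 90-95% of the months 3-24 follow-up.
- Footnote 7 does not prove that follow-up after failure was intended, since sections 4 and 4.1 allow hormonal therapy without failure.
- Under section 6.1, after 30 days only serious related events need recording for any patient. The adverse-event loss is therefore mainly new serious late events.

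None of this supplies the missing exception. As written, a patient with recurrence goes off study, and no section continues late safety or questionnaire collection.

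**Conclusion.** The point holds as a conflict between sections that should be reconciled. Its harm is moderate and mainly affects the secondary and exploratory objectives. On the biochemical reading, and under a constant hazard at the cited rates, about 9-18% of patients would leave before month 24, at most about 4-9 of 48. Later patient-reported scores and end-of-follow-up regret would come mainly from patients with controlled disease, so regret after unsuccessful salvage would be weakly informed.

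The late Grade 4 or higher rule loses about 1-7 points of sensitivity in six patients. That rests on assumed true rates of 10-30%, 2-year failure of 8.5-17.4%, and events spread evenly and independent of failure. The loss is under 2 points at 9% or below, and larger if events cluster late or failure is more frequent. It always runs towards missing a signal. The documents do not support a claim that the acute MTD assessment or bPFS is compromised.

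**What to change.** Reconcile 3.7.2 with 3.1.1, 3.3 and 8.4:

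- Define recurrence in 3.7.2, stating whether it is biochemical recurrence as in 6.3.2 or clinical recurrence.
- Let recurrence end PSA response assessment only. State that radiation-attributable late adverse events and questionnaires continue to month 24, and that the remote contact in footnote 7 applies to these patients.
- Record the dates of recurrence and of any further therapy, and say in 8.4 that data after those dates will be flagged.

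The cost is a short amendment and a few extra remote contacts and questionnaires. Some of the added data will follow other treatment and will need care in attribution. The sample size, dose levels and escalation rules do not change.

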3.7.3 Lost to Follow-up

A participant will be considered lost to follow-up if he or she fails to return for 3 scheduled visits and is unable to be contacted by the study site staff.

Abbreviated Title: Image guided radiation

Version Date: 06/03/2024

The following actions must be taken if a participant fails to return to the clinic for a required study visit:

- The site will attempt to contact the participant and reschedule the missed visit and counsel the participant on the importance of maintaining the assigned visit schedule and ascertain if the participant wishes to and/or should continue in the study.
- Before a participant is deemed lost to follow-up, the investigator or designee will make every effort to regain contact with the participant (where possible, 3 telephone calls and, if necessary, an IRB approved certified letter to the participant's last known mailing address or local equivalent methods). These contact attempts should be documented in the participant's medical record or study file.
- Should the participant continue to be unreachable, he or she will be considered to have withdrawn from the study with a primary reason of lost to follow-up.

4 CONCOMITANT MEDICATIONS/MEASURES

Supportive care with blood components, antibiotics, analgesics, and general medical therapy will be provided if the need relates to the performance of protocol assessments (imaging procedures) or to treat side effects of therapy. Every effort will be made to refer the patient to their collaborating physician in the community for care unrelated to the protocol therapy or procedures. There are no limitations on the type of non-investigational concurrent medications allowed, as in general, these patients do not receive additional therapy for prostate cancer after radiotherapy, with the exception of hormonal therapy, which may be delivered as per the current standard of care.

Radiation related side effects will be managed as per the current standard of care without restrictions in medications or procedures that may be performed for management.

4.1 ADT

We will allow patients to receive ADT on this trial after enrollment if deemed clinically appropriate, as the bulk of data suggests that it has no impact on the toxicities we have defined as DLTs in this trial.

ADT will be delivered on this protocol as per the current standard of care with the duration of therapy to be determined by the treating physician if indicated. This may include an anti-androgen, gonadotropin releasing hormone agonist, or the combination of both. As an alternative, patients may also receive ADT through their local care provider (medical oncologist, primary care physician, urologist) in collaboration with the research team.

5 CORRELATIVE STUDIES FOR RESEARCH

5.1 BIOSPECIMEN COLLECTION

Test/assay	Volume blood (approx)	Type of tube ^a	Collection point	Location of specimen analysis
ELISA/Bioplex analysis of predictive biomarkers	Plasma 8 mL	EDTA (lavender top)	See Study Calendar 3.3	[name]
Circulating DNA by whole genome sequencing with copy number analysis	5-10 mL	STREK	See Study Calendar 3.3	[name]
Exosome analysis (Surface receptor analysis by Nano FACS, RNA analysis)	Plasma 8 mL	EDTA (lavender top)	Study Calendar 3.3	[name]
Immune cell subsets and circulating endothelial cells by FACS	Whole blood 16 mL	CPT citrate	Study Calendar 3.3	DTB Clinical Translational Unit
ELISA analysis of predictive biomarkers	Urine 15 mL	Sterile cup	Study Calendar 3.3	[name]
Whole genome sequencing	If available, tissue blocks or sections from prostatectomy or biopsies		Baseline	[name]
a. Please note that tubes and media may be substituted based on availability with the permission of the PI or laboratory investigator.				

A number of exploratory correlative studies will be performed. These studies focus on two main areas: assessment of tumor radiation response (disease control) and prediction of normal tissue toxicity. Plasma and urine will be analyzed for the presence of markers of prostate cancer that

were initially described from proteomic analysis of prostate cancer patient's blister samples from protocol 09-C-0120. A number of candidate markers were identified during the discovery proteomic analysis, and the plasma samples from this trial will be used to test these markers without the complication of residual normal prostate tissue which may impact their suitability as a biomarker of cancer post-radiation. The post-prostatectomy setting provides an excellent minimal disease state to test candidate biomarkers.

5.1.1 Circulating immune cells during radiotherapy

During a course of radiotherapy, the target tissue is irradiated, including local immune cells. It is well known that radiation can cause changes in the local immune landscape, an effect that has been considered a major contributor to radiation injury [42-44]. Importantly, radiation can be considered immunosuppressive or immune activating depending on the field size, portion of the body targeted, and fractionation employed [45-48]. Recently, there has been tremendous interest in leveraging local and systemic immune changes caused by radiotherapy to enhance immunotherapy for cancer [49-54].

One previously observed change in immune cell subsets after irradiation is a change in the number and proportion of lymphocyte subsets, particularly CD4+ T cells and CD8+ T cells. Treatment induced lymphopenia can be quite striking in patients treated with combined radiation and chemotherapy [55, 56]. In elderly patients with high grade glioma, severe treatment related lymphopenia has been shown to correlate to inferior survival [57]. Treatment related lymphopenia has been observed in patients treated with post-prostatectomy radiotherapy with conventionally fractionated or moderately hypofractionated (2.35 Gy per fraction) approaches [58]. Although this report did not further classify lymphocyte subsets, we have accumulated data in anal cancer patients (Figure 1) and prostate cancer patients treated with radiotherapy on ROB protocols that suggests that CD4+ cells are disproportionately affected by radiotherapy +/- chemotherapy compared to other lymphocyte subsets. In our experience, the suppression of circulating lymphocyte subsets in prostate cancer patients is evident, but more variable in intensity and duration than what is seen when chemotherapy is delivered.

[figure not shown]

Figure 1. Treatment related lymphopenia. Immune cell subsets in HIV negative patients that receive Mitomycin-C, 5-fluorouracil, and radiation for anal cancer (protocol 11-C-0129). Radiation treatment was completed by 42 days. Total WBC (A), lymphocyte count (B), CD4+ T cells (C), and CD8+ T cells (D) were

assessed at multiple time points. Lines represent the trajectory for each patient. Toxicity grade (CTC AE) for each measure is noted.

Based on these findings, we are interested in more comprehensively evaluating lymphocyte subsets in this patient cohort. This trial will also allow us to begin to ask, in an exploratory fashion, if more aggressive hypofractionation and the volume irradiated alters the degree of lymphopenia. These are areas of substantial interest to the radiation oncology and immunotherapy community.

Macrophages also are known to play a critical role in radiation injury and the immune environment after irradiation [42-44, 59]. Radiation is known to deplete tissue resident macrophages, resulting in recruitment of bone marrow derived monocytes to repopulate [60]. Further, the polarization of monocytes/macrophages and lymphocytes is known to impact radiation toxicity [42, 61]. This trial will assess immune the subsets and polarization over time, in an exploratory fashion. We envision that these findings may spur additional clinical and laboratory research studies. Similarly, circulating endothelial cells will be analyzed before, at the end of, and one month after radiation in a purely exploratory fashion.

Immune cell subsets and polarization will be analyzed at several timepoints throughout the protocol in an exploratory fashion. Peripheral blood mononuclear cells (PBMC) will be assessed using multiparameter flow cytometry for conventional CD4+ T-cells, CD8+ T-cells, Tregs, monocyte subsets and MDSC populations. Assessment may include functional markers, i.e. PD-1, TIM-3, CTLA-4, CD40. PBMC will be analyzed for forward and side scatter, and a dump channel will be created to exclude cells expressing hematopoietic markers, such as CD45. Endothelial cells will be identified using co-expression of markers, such as CD31 and CD146 for mature endothelial cells and CD31 and CD133 for circulating endothelial progenitor cells (CEP). The cell populations will also be analyzed for viability using scatter profiles and a vital stain (e.g., Hoechst 33258). Percentages of stained cells will be determined and compared with appropriate negative controls.

